3.2.1 Secondary Clinical Efficacy Endpoints

1. Occlusive material burden using the Venous Volumetric Index (VVI) Score¹¹, measured at Baseline and Post-EkoSonic® Study Treatment Procedure, both as a continuous measure and as a binary variable for achievement of a ≥ 5 point reduction from Baseline to Post-Procedure.
2. Change in Villalta score from Baseline to 90 days, 180 days, and 365 days Post-EkoSonic® Study Treatment Procedure, both as a continuous measure and as a binary variable for having achieved a ≥ 4 point reduction from Baseline.
3. Absence of re-occlusion at 365 days of the treated segment, as documented by duplex imaging.
4. Change in SF-36 Quality of Life (QoL) and Physical Component Summary (PCS), CEAP classification, VEINES-QOL, and VCSS from Baseline to 30, 90, 180 and 365 days Post-EkoSonic® Study Treatment Procedure.
5. Symptomatic PTS-induced admission to emergency room or unplanned visit to physician office or hospitalization from Post-EkoSonic® Study Treatment Procedure up to 365 days thereafter
6. Time from starting initial thrombolytic infusion to discharge from hospital

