4.6 Revascularization

If, at any time during the follow-up period a subject is found to have re-occlusion of a venous segment that is associated with escalation of symptoms, the subject may undergo revascularization using any method the treating physician feels is appropriate. The subject shall remain in the study and shall attend all planned follow-up visits. All revascularization procedures shall be documented on the revascularization case report form.

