6.0 STATISTICAL ANALYSIS

6.1. Analysis Subject Sets, Evaluable Subjects and Missing Data Handling Convention

Efficacy Evaluable Segments are defined as DVT segments from enrolled subjects which: (a) were successfully crossed and received EkoSonic® Treatment, and (b) had Villalta scores available at both Baseline and 30 days Post-EkoSonic® Treatment visit. The **Efficacy Segment Set** includes all efficacy evaluable segments and will be used for all segment specific efficacy analyses. A treated segment that received a revascularization procedure within 30 days Post-EkoSonic® Treatment will be regarded as a failure for the primary efficacy endpoint, i.e. without a ≥ 4 -point reduction in Villalta score from Baseline to 30 days Post-EkoSonic® Treatment.

Efficacy Evaluable Subjects are defined as enrolled subjects for whom at least one affected segment: (a) was successfully crossed and received EkoSonic® Treatment, and (b) had Villalta scores available at both Baseline and 30 days Post-EkoSonic® Treatment visit. The **Efficacy Subject Set** includes all efficacy evaluable subjects and will be used for all subject specific efficacy analyses such as for quality of life measures.

Safety Subject Set

Safety evaluable subjects are defined as enrolled subjects for whom the EkoSonic® Treatment was initiated, i.e. venous access attempted for catheter introduction. The **Safety Subject Set** includes all safety evaluable subjects and will be used for all safety analyses.

Missing data will not be imputed for the primary efficacy and safety analyses. However sensitivity analyses may be performed to assess the robustness of study results with respect to missing data.

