6.2.2 Efficacy

Efficacy analyses will be performed on the Efficacy Segment Set or Efficacy Subject Set as appropriate for the nature of the data.

Primary Clinical Efficacy Analysis:

The 30 day Villalta score change from Baseline will be analyzed as a binary variable for a segment's status as having achieved a ≥ 4 point reduction or not. Study success will be defined by $\geq 50\%$ of the efficacy evaluable segments achieving at least a 4 point reduction. In addition, as a continuous measure, change in Villalta score from Baseline to 30 day Post-EkoSonic® Treatment will also be summarized and analyzed as described above in 6.2.1 General Methodology.

Primary Technical Efficacy Analysis:

The change in blood flow calculated by time to washout in the affected segment from Baseline and Post-EkoSonic® Treatment will be analyzed as a continuous measure. A statistically significant (2-sided $p < 0.05$) improvement in flow rate, i.e. reduction in time to washout, will be considered a success for the study.

Secondary Efficacy Analyses:

For all secondary efficacy endpoints described in Section 3.2.1, i.e. VVI score change from Pre- EkoSonic® Treatment to Post-Treatment, Villalta score change from Baseline to 90, 180, and 365 days, re-occlusion rate up to 365 days, change from Baseline to all follow-up time points for SF-36 QOL and PCS component scores, CEAP classification, and VCSS, occurrences of symptomatic PTS-induced admission to emergency room or unplanned visit

to physician office or hospitalization from post EkoSonic® Treatment up to 365 days thereafter, time from starting initial thrombolytic infusion to discharge from hospital, analyses will be performed as described above in 6.2.1 General Methodology. For symptomatic PTS-induced healthcare utilization, time to event analyses will be performed for days from EkoSonic® Treatment to first occurrence for each of (a) admission to emergency room, (b) unplanned visit to physician office, and (c) hospitalization.

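### Revascularization counts as failure only for the 30-day primary endpoint, so a re-treated limb can count as an EkoSonic responder at 90, 180 and 365 days

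*Protocol*

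**What the plan says.** Four parts of the protocol bear on this.

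- **Section 6.1** sets the counting rule: "A treated segment that received a revascularization procedure within 30 days Post-EkoSonic® Treatment will be regarded as a failure for the primary efficacy endpoint". It names one endpoint and one time window.
- **Section 4.6** concerns re-occlusion with worsening symptoms at any time in follow-up. It says that "the subject may undergo revascularization using any method the treating physician feels is appropriate", and then: "The subject shall remain in the study and shall attend all planned follow-up visits". It adds: "All revascularization procedures shall be documented on the revascularization case report form".
- **Section 3.2.1, item 2** lists as a secondary endpoint: "Change in Villalta score from Baseline to 90 days, 180 days, and 365 days Post-EkoSonic® Study Treatment Procedure". This is taken as a continuous measure and also "as a binary variable for having achieved a ≥ 4 point reduction from Baseline". No condition about re-treatment is attached.
- **Section 6.2.2** says of the secondary endpoints that "analyses will be performed as described above in 6.2.1 General Methodology". Section 6.2.1 summarizes the Efficacy Segment Set at each time point and does not mention revascularized segments.

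No other part of the protocol extends the 6.1 rule. Section 6.2.1 leaves further analysis detail to a statistical analysis plan, which is not at hand.

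**The concern.** The protocol accepts a principle: a limb that needed a second procedure is not a success of the first. It applies this at Day 30 and not to the same ≥4-point endpoint later, although most of the follow-up time in which re-treatment can happen lies after Day 30.

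The limbs concerned are not a random subset. Under section 4.6 they are re-treated because the vein has re-occluded and symptoms have escalated. If the second procedure helps, the improved score is credited to EkoSonic treatment at the next visit. A limb revascularized on Day 20 is a failure at Day 30 whatever its score, yet can be a responder at Day 90 because of the second procedure.

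The study has one arm, so no control group would reveal this. A responder rate that holds steady or rises between Day 30 and Day 365 could reflect lasting benefit, re-treatment of failures, or both, and the planned analysis would not separate them.

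**Working it through.** **1. The plan's own figures.** Section 6.2.4 takes 70 independent segments and success at ≥50%, that is 35 or more. The exact binomial gives:

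- P(X ≥ 35 | n = 70, p = 0.55) = 0.832, against 0.83 stated.
- P(X ≥ 35 | n = 70, p = 0.39) = 0.040, against ≤0.04 stated.

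Both reproduce. Both concern only Day 30, where the revascularization rule already applies, so this point does not change them.

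**2. How one limb is counted.**

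| Limb | Day 30 | Day 90, 180 or 365 |
|---|---|---|
| Never re-treated | by score | by score |
| Re-treated by Day 30 | failure, whatever the score | by score |
| Re-treated after Day 30 | by score | by score, including visits after re-treatment |

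**3. Effect on the later responder rate.** For a given visit let

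- r = share of limbs re-treated before the visit,
- q = share of those whose score at the visit is ≥4 points below Baseline,
- b = response rate among limbs not re-treated.

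Rate by score alone = (1 − r)b + rq.
Rate with the 6.1 rule extended = (1 − r)b.
Difference = r × q, which does not depend on b.

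**4. Size.** The protocol gives neither r nor q, so the values below are assumptions. Limb counts use the 70 of section 6.2.4. Enrolment may reach 200 evaluable subjects, which changes the counts but not the percentage points.

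| r | q | Difference r × q | Limbs of 70 |
|---|---|---|---|
| 5% | 40% | 0.05 × 0.40 = 2 points | 1.4 |
| 10% | 60% | 0.10 × 0.60 = 6 points | 4.2 |
| 20% | 70% | 0.20 × 0.70 = 14 points | 9.8 |

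For the middle row with b assumed to be 50%: by score alone, 0.90 × 0.50 + 0.10 × 0.60 = 51%; with re-treated limbs as failures, 0.90 × 0.50 = 45%.

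**5. Continuous measures.** Villalta, VCSS and CEAP changes after re-treatment also mix the effects of two procedures. Dropping the post-revascularization values is not a safe remedy, because the limbs removed are selected for worsening. As an illustration, let 63 limbs improve by 5 points and 7 re-treated limbs by 2. The mean over all limbs is (63 × 5 + 7 × 2)/70 = 329/70 = 4.7. After exclusion it is 5.0. The exclusion makes the result look better.

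**The case against.** **This belongs in the statistical analysis plan.** Handling of re-treatment for secondary endpoints is often left there, and the unseen plan could contain a rule. That possibility stands. But the protocol does not leave the matter open: it states a rule, confines it to one endpoint, and defines the later responder endpoints without it. A plan that extended the rule would be adding a condition to the protocol's own definition.

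**Observed scores are a legitimate target.** Scoring every limb whatever later care it received answers a real question, and keeping re-treated subjects on all visits fits it. This also stands, and is why the observed-score rate should still be shown. What does not stand is using one counting rule at Day 30 and another later for the same endpoint, without saying so. The word overstated here means relative to the protocol's 30-day rule. Section 4.6 requires escalating symptoms, not loss of the 4-point gain, so some re-treated limbs may still have been responders when re-treated. The product r × q is therefore the exact gap between two counting rules, not an estimate of what re-treatment added.

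**Durability is measured elsewhere.** A reader might infer that the later Villalta visits are the only evidence of durability. They are not. Section 3.2.1 also lists absence of re-occlusion and PTS-related healthcare use, and section 6.2.2 gives time-to-event analyses for the latter. The re-occlusion endpoint offers partial protection: section 6.2.2 speaks of the rate up to 365 days, which would capture a re-treated limb, whereas section 3.2.1 item 3 reads the status at 365 days, when a re-treated vein could be open again.

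**Not every re-treated limb becomes a responder.** A reader might infer that all such limbs enter as successes at every later visit. The text does not support that. A limb counts only if its score at that visit is at least 4 points below Baseline.

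**Conclusion.** The point holds for the secondary responder endpoints at 90, 180 and 365 days. The protocol applies its revascularization rule at Day 30 and defines the same binary endpoint at later visits without it. For that endpoint the difference runs one way: counting by score alone can never give a lower responder rate than the 6.1 principle would.

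The size is r × q. It is 2 to 14 percentage points if 5–20% of limbs are re-treated before the visit and 40–70% of those score as responders. Both ranges are assumptions, and if few limbs are re-treated the effect is small.

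A reader might infer that trial success is at risk. It is not: the primary endpoint, its ≥50% criterion and the 0.83 probability are untouched, and the secondary endpoints carry no success threshold. This is an improvement that should be made, not a flaw that undermines the study. It concerns only how outcomes are counted, not whether or how a limb should be revascularized.

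**What to change.** Extend the sentence in section 6.1 along these lines: a treated limb that received any revascularization before a visit's Villalta assessment is a failure for the binary ≥4-point endpoint at that visit and at all later visits. Refer to this rule in section 3.2.1 item 2 and in section 6.2.2.

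Alongside it:

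- Report the number of re-treated limbs by visit.
- Show the responder rate from observed scores as a supportive analysis.
- For the continuous Villalta, VCSS and CEAP changes, keep the summary of all observed values and do not simply drop values after revascularization. If a companion analysis is wanted, carry forward the last value before revascularization, or the Baseline value.

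The cost is an added sentence, a supportive table, and later responder rates that are somewhat less favourable. No data are needed beyond the revascularization case report form. Section 4.6 does not list that form's fields, so confirm that it records the date and the limb.

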3.1.1 Primary Clinical Efficacy Endpoint

Clinical efficacy will be evaluated using the Villalta score at Baseline compared to 30 days Post-EkoSonic® Study Treatment Procedure. Study success will be defined by ≥50% of the efficacy evaluable limbs achieving at least a 4 point reduction.

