4.5 Subject Withdrawal

Subjects may withdraw from participation at any time during the clinical study. All data collected prior to withdrawal shall remain part of the study. Every effort shall be made to encourage the subject to remain in the trial. If the subject declines, determine and document the reason for withdrawal.

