6.2.4 Power Estimation

For the primary efficacy endpoint of change in Villalta score at 30 days from Baseline, study success will be defined by $\geq 50\%$ of the evaluable DVT segments achieving at least a 4 point reduction. Assuming the true underlying proportion of such segments to be 55%, the probability for observing a $\geq 50\%$ success proportion in a study with 70 evaluable independent segments is 0.83. On the other hand, should true underlying success proportion be $<40\%$, e.g. 39%, the probability for observing a $\geq 50\%$ success proportion in 70 independent segments is ≤ 0.04 .

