7.0 RISK ANALYSIS

7.1 Description and Analysis of Risks

The risks that are associated with use of the EkoSonic® Endovascular System are expected to be the same as the risks associated with the placement of any catheter into the venous system including vessel injury such as dissection, perforation, or rupture and are listed in the IFU Appendix A. Potential risks associated with thrombolytic drugs are listed in the package insert for alteplase (Appendix B). Potential risks for subjects undergoing the procedure are listed in the following table.

Table 1 Anticipated Adverse Events During EkoSonic® Treatment

Adverse Event	Definition
Amputation	Surgical removal of any portion of the involved leg, foot or toes.
Arrhythmia	Irregularity or loss of rhythm of the heartbeat requiring treatment with drugs, cardioversion, or pacemaker.
Bleeding – Access site	Clinically significant bleeding at the catheter access site
Bleeding - Other	Clinically significant bleeding at any site other than the access site
Congestive Heart Failure	Development of an acute episode of or exacerbation of existing low cardiac output accompanied by distal and/or pulmonary edema requiring tracheal intubation or Intensive Care Unit care.
Contrast Reaction	Documented reaction directly attributed to contrast medium used during the angiography or venography.
Death	All deaths should be reported regardless of cause
DVT – Recurrent, same limb	A new episode of DVT in the study limb. If subject was discharged, any returns for DVT symptoms will be considered recurrent.
DVT – Recurrent, other	A new episode of DVT in a non-study limb.
Device Issue	Any device operation / malfunction that results in a negative clinical occurrence for the subject. Failure to lyse or automatic shut off as outlined in the IFU will not be considered a Device Issue.
Distal Embolization	Filling defect with an abrupt 'cutoff' in one of the peripheral vessels distal to the site of treatment.
Dyspnea	Labored or difficult breathing
Embolism	Blockage of a vessel by dislodged thrombus confirmed by angiography
Hematoma - Access site	Clinically significant localized collection of blood at catheter access site
Hematoma - Other	Clinically significant localized collection of blood at any site other than access site
Infection - Systemic	Systemic infection as indicated by increase in white blood cell count sufficient to warrant antibiotic therapy.

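### A treated limb lost before Day 30 through death, or an amputation that prevents scoring, is dropped from the primary responder rate instead of counted as a non-response

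*Protocol*

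**What the plan says.** Protocol 3.1.1 sets the decision rule: "Study success will be defined by ≥50% of the efficacy evaluable limbs achieving at least a 4 point reduction". It is an observed proportion, with no test or confidence bound attached; 6.2.2 repeats it for segments.

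Protocol 6.1 defines what enters that proportion. The segment must have been crossed and treated, and must have "had Villalta scores available at both Baseline and 30 days Post-EkoSonic® Treatment visit". On missing scores the section says "Missing data will not be imputed for the primary efficacy and safety analyses", followed by "However sensitivity analyses may be performed to assess the robustness of study results with respect to missing data". One early event is assigned an outcome: "A treated segment that received a revascularization procedure within 30 days Post-EkoSonic® Treatment will be regarded as a failure for the primary efficacy endpoint".

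Other ways of losing the score are foreseen elsewhere:

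- Section 4.5: "Subjects may withdraw from participation at any time during the clinical study".
- Table 1 in 7.1 lists death and amputation among the anticipated adverse events. Amputation is defined as "Surgical removal of any portion of the involved leg, foot or toes".
- Sections 4.2.6 and 8.7.1 collect a Villalta score at early termination, but no section says whether it can stand in for the Day-30 score.

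**The concern.** Read together, these rules delete a treated limb whose subject dies before Day 30, or whose leg can no longer be scored after amputation. Neither limb can have achieved the 4-point reduction. Section 6.1 already accepts that a bad early event should count against the treatment, since it does so for early revascularization, but it stops there.

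The revascularization rule is itself incomplete. If a revascularized limb has no Day-30 score, one sentence calls it a failure while the entry condition removes it from the set.

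The study has one arm and is decided by a raw proportion, so no control group has losses that might offset these. Each non-responder removed raises the observed rate directly. The treatment of such limbs is fixed in 6.1, so a statistical analysis plan could not count them as failures in the primary analysis without contradicting the protocol.

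**Working it through.** **Inputs from the protocol.** Section 6.2.4 gives 70 evaluable independent segments, a 55% true rate with success probability 0.83, and a 39% true rate with success probability at most 0.04. The success rule is at least 50%, so 35 of 70. The synopsis and section 4.0 allow up to 200 evaluable subjects.

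**Assumptions.** No rate of loss before Day 30 is stated, so a range is used. Limbs are treated as independent, as in 6.2.4.

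**Step 1: reproduce the stated figures.** With X binomial:

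- P(X ≥ 35 | n = 70, p = 0.55) = 0.832
- P(X ≥ 35 | n = 70, p = 0.39) = 0.040

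Both agree with 6.2.4.

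**Step 2: worst case at 70 evaluable limbs.** Let m further treated limbs be lost, all non-responders, with a true rate of 39% in all 70 + m treated limbs. The rate among evaluable limbs is 0.39 × (70 + m) / 70.

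| Lost limbs m | m / (70 + m) | Rate among evaluable | P(X ≥ 35 of 70) |
|---|---|---|---|
| 0 | 0% | 0.390 | 0.040 |
| 1 | 1.4% | 0.396 | 0.049 |
| 2 | 2.8% | 0.401 | 0.060 |
| 4 | 5.4% | 0.412 | 0.086 |
| 8 | 10.3% | 0.435 | 0.163 |

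**Step 3: milder assumption.** If 4 lost limbs respond at half the overall rate (0.195), the evaluable rate is (0.39 × 74 − 4 × 0.195) / 70 = 0.401. The chance is then 0.060, not 0.086. If lost limbs respond at the full 39%, the evaluable rate is 0.39 and there is no bias.

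**Step 4: larger samples, worst case again.** With a fraction d of treated limbs lost, the evaluable rate is 0.39 / (1 − d): 0.411 at d = 5% and 0.433 at d = 10%.

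| Evaluable limbs | Responders needed | No loss | 5% lost | 10% lost |
|---|---|---|---|---|
| 150 | 75 | 0.004 | 0.017 | 0.059 |
| 200 | 100 | 0.001 | 0.0065 | 0.034 |

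**Step 5: how easily a result would turn.** With x responders in 70, the smallest m giving x / (70 + m) < 0.5 is m = 2x − 69. That is 1 lost limb at 35/70 (35/71 = 49.3%), 3 at 36/70, 5 at 37/70, 7 at 38/70 and 9 at 39/70.

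**Step 6: effect of keeping lost limbs as failures.** Take 70 treated limbs, 4 of them lost non-responders, and a true rate of 39% in all 70. The evaluable rate is 0.39 × 70 / 66 = 0.414. The present rule needs 33 of 66 and passes with probability 0.097. With the lost limbs kept as failures, 35 responders are needed among the same 66, and the probability is 0.037.

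**The case against.** The strongest reply is that the evaluable set is an explicit choice, stated in the synopsis and in 3.1.1, 6.1 and 6.2.2. Deaths are not hidden either: 6.2.3 reports them through 365 days in everyone in whom venous access was attempted. That is true, but a safety table does not enter the success rule.

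Four stronger readings are tempting, and the protocol does not support them.

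- **That every withdrawal biases the result toward success.** Nothing in 4.5 indicates how those who withdraw respond. If they respond as often as completers, only sample size is lost.
- **That every amputation removes the score.** The Table 1 definition extends to toes, and a leg without a toe may still be scorable. Only an amputation that prevents scoring matters here.
- **That the 0.04 in 6.2.4 is wrong.** It is stated for evaluable segments and is correct for them. It simply does not carry over to all treated limbs.
- **That false success would really reach 0.09 to 0.16.** Those figures need 4 to 8 lost limbs, all non-responders, at 70 evaluable limbs. Eligibility excludes life expectancy under one year, active cancer and high risk of catastrophic bleeding, so few certain non-responders may arise by Day 30.

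It can also be said that a revascularized limb usually has a score, only a contaminated one, so that rule addresses a different problem. This has some force, but does not explain why a death should be dropped. Finally, naming a missing-data sensitivity analysis is commonly left to the statistical analysis plan. On its own, the optional wording would not be a finding; the point rests on the primary rule.

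**Conclusion.** The point holds in a narrow form. As written, 6.1 removes from the primary rate treated limbs that are certain non-responders: deaths, and amputations that prevent scoring, before Day 30. For these the direction is certain and favours success. For withdrawals it is conditional on a lower response than in completers.

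The size cannot be fixed, because no loss rate is given. At 70 evaluable limbs and a 39% true rate, one such loss moves the chance of passing from 0.040 to 0.049 and two to 0.060; larger shifts are a worst case. At 200 evaluable limbs the worst case stays below 0.04 at 10% loss, though at 150 it reaches 0.059. The practical risk lies in a result close to 50%, where one to a few lost limbs decide the outcome. This is a modest defect that is cheap to remove.

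**What to change.** In 6.1, extend the sentence on early revascularization. A crossed and treated limb with no Day-30 Villalta score because of death, or of an amputation that prevents scoring, counts as not achieving the reduction of at least 4 points and stays in the primary denominator. The same applies to a revascularized limb with no Day-30 score.

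Replace the optional sensitivity wording with one required analysis that counts every treated limb without a Day-30 score, including all withdrawals, as a failure. Withdrawals then need no sorting by recorded reason, which would be an unblinded judgement.

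**Cost.** One sentence, one table, no new data, and a slightly less favourable responder rate if such losses occur. If 55% is the rate among 70 evaluable limbs, one or two losses raise the responders needed from 35 to 36, and the chance of success falls from 0.83 to 0.77. If 55% is the rate in all 70 treated limbs, with 2 of them lost, it is 0.84. Section 6.2.5 records that the interim futility look on this endpoint has been done, so the amendment should state that the change was made after it.
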